10.5.3. Exploratory Analysis for Immunogenicity

To evaluate the possible impact on the immunogenicity endpoints of a population not balanced by age and gender, exploratory analyses will be conducted using linear regression to compare the

AV7909 Anthrax Vaccine

IND 014451

Protocol EBS.AVA.210, Version 3.0 (28 October 2019)

immunogenicity response at Day 37 between each AV7909 + antibiotic group and the AV7909 only group, ie, between Group 1 (AV7909 + ciprofloxacin) and Group 3 (AV7909) and between Group 2 (AV7909 + doxycycline) and Group 3 (AV7909). In the linear regression models, the stratification factor, study site, will be included in the model as a random effect; participant sex and age will be included as fixed factors with age being dichotomized into ≤ 30 and >30 . The adjusted GMT ratios for the TNA NF₅₀ values will be provided with 95% CI.

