## **4.6 Adjustment for Covariates**

An exploratory immunogenicity linear regression analysis will be conducted with adjustment for site, and covariates age and sex, as specified in [Section 7.2.1](#).

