## **4.7 Subgroup Analysis**

For immunogenicity analysis, TNA NF50 values will be summarized by treatment group and each of the following classification variables (categories are defined in the parentheses):

- Age (18 - 30, 31 - 45)
- Sex (Male, Female)

No statistical testing will be performed for subgroup analyses.

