## 7.2 Secondary Immunogenicity Endpoints

The secondary immunogenicity analysis is aimed to assess whether the immunogenicity of AV7909 two weeks following the final dose of a two-dose vaccination series is affected by concomitant dosing with oral ciprofloxacin or doxycycline.

Non-inferiority test will be constructed using the GMT ratio of TNA NF50 (Group 1/Group 3 or Group 2/Group 3) between IP group with participants that received both AV7909 and ciprofloxacin or doxycycline (Group 1 or 2) and the IP group with participants that received AV7909 only (Group 3). Point estimate and the 95% CI for the GMT ratio will be estimated using the linear regression based on log10 transformed TNA NF50 with equal variance. If the lower bound of the two-sided 95% CI of geometric mean ratio is greater than the non-inferiority margin of 0.5, it is concluded that the immune response in the group who received AV7909 plus either ciprofloxacin or doxycycline is non-inferior to the group which received AV7909 alone and thus that either ciprofloxacin or doxycycline did not demonstrably affect the immunogenicity of AV7909.

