### 7.2.1 Exploratory Analysis for Immunogenicity

To evaluate the possible impact of imbalance in sex and age on the immunogenicity endpoints, exploratory analyses will be conducted using linear regression to compare the immunogenicity response at Day 37 between each AV7909 + antibiotic group and the AV7909 only group, i.e., between Group 1 (AV7909 + ciprofloxacin) and Group 3 (AV7909) and between Group 2 (AV7909 + doxycycline) and Group 3 (AV7909). In the linear regression models, the stratification factor, study site, will be included in the model as a random effect; treatment group, participant sex and age will be included as fixed factors with age being dichotomized into ≤30 years and >30 years. The adjusted GMT ratio for TNA NF50 will be provided with 95% confidence interval. Any differences between the exploratory (adjusted) and the primary (unadjusted) analyses will be discussed in the final CSR.

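### The deciding TNA non-inferiority regression is unadjusted; prespecifying sex and age in it would add precision and robustness at almost no cost

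*Protocol*

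**What the plan says.** SAP 7.2 defines the formal test: "Point estimate and the 95% CI for the GMT ratio will be estimated using the linear regression" on log10 NF50 with equal variance, and the lower 95% limit is compared with 0.5. Neither that section nor protocol 10.5.2 names a covariate. SAP 7.2.1 removes any doubt about how the formal analysis is meant: "Any differences between the exploratory (adjusted) and the primary (unadjusted) analyses will be discussed in the final CSR".

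Adjustment is confined to the exploratory model. SAP 4.6 states: "An exploratory immunogenicity linear regression analysis will be conducted with adjustment for site, and covariates age and sex". Protocol 10.5.3 gives the form ("participant sex and age will be included as fixed factors with age being dichotomized" at 30 years, with site as a random effect) and the purpose: "To evaluate the possible impact on the immunogenicity endpoints of a population not balanced by age and gender". Elsewhere age and sex appear only in subgroup summaries, for which SAP 4.7 says: "No statistical testing will be performed for subgroup analyses".

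Randomisation is stratified by site alone (protocol 4.1, SAP 2.5.1). The targets of 40-60% male and 40-60% in each of the age bands 18-30 and 31-45 are requests to sites about recruitment, not limits within each arm. Age in years is available, since SAP 5.3.1 summarises it as a continuous variable.

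**The concern.** Nothing in the allocation scheme balances sex or age between arms, so the arms can differ on both by chance. The plan foresees this but leaves the adjustment out of the analysis that decides non-inferiority. If the adjusted and unadjusted lower limits fell on opposite sides of 0.5, the unadjusted one would decide and the difference would only be discussed in the report. In an open-label trial, a change of the deciding model after the data are seen would carry little weight, so the choice has to be made in advance.

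In a linear model on the log scale, adjusting for baseline covariates does not change what the GMT ratio means. It removes the chance imbalance in those covariates and shrinks the residual variance. What is at stake is the width of the interval and the stability of the estimate, not the error rate of the test.

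**Working it through.** **Inputs.** From protocol 10.2 and SAP 2.4: true ratio 0.85, margin 0.5, CV 100%, one-sided 2.5%, 53 evaluable and 70 planned per group. The share of log-titre variance explained by sex and age (R²) is not in the documents; 5%, 10% and 15% are assumed.

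**The plan's own figure.** Log-scale SD = √ln(1 + 1²) = √ln 2 = 0.8326. Distance to the margin = ln(0.85/0.5) = 0.5306. At 53 per group, SE = 0.8326 × √(2/53) = 0.1617 and the noncentrality is 0.5306/0.1617 = 3.28. The noncentral-t power is 90.2% at 53 and 89.6% at 52, so the stated 53 reproduces. It was reached without adjustment.

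**Effect of adjustment.** The residual SD becomes 0.8326 × √(1 − R²), and the interval on the log scale narrows by the same factor.

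| R² (assumed) | CI width factor | Power, 53 per group | Power, 70 per group |
|---|---|---|---|
| 0 | 1 | 90.2% | 96.3% |
| 5% | √0.95 = 0.975 | 91.5% | 97.0% |
| 10% | √0.90 = 0.949 | 92.9% | 97.7% |
| 15% | √0.85 = 0.922 | 94.1% | 98.2% |

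Spending two more degrees of freedom changes these powers only in the second decimal of a percentage point.

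**Size of chance imbalance.** With half of each arm male, the 95% range of the between-arm difference in the proportion male is ±1.96 × √(2 × 0.25/53) = ±19 percentage points at 53 per arm, and ±17 at 70. If sex alone explained 5% of the variance (assumed), men and women would differ by 2 × 0.8326 × √0.05 = 0.372 on the log scale. A 19-point imbalance would then shift the ratio by a factor of exp(0.19 × 0.372) = 1.07.

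**Validity.** In a simulation of 20,000 trials at 53 per arm, with R² of 5% or 20% split equally between age and sex and ages flat over 18-45, type I error was 0.022 to 0.025 for the unadjusted, cut-age and continuous-age models alike.

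**The age cut in the exploratory model.** For whole-year ages spread evenly over 18-45, the variance of age is (28² − 1)/12 = 65.25. Within the bands it is (13² − 1)/12 = 14.0 for 18-30 and (15² − 1)/12 = 18.67 for 31-45, a weighted mean of (13 × 14.0 + 15 × 18.67)/28 = 16.5. The cut therefore leaves 16.5/65.25 = 25% of the variance of age within bands. The documents give no age distribution; other assumed shapes gave 12% (U-shaped) to 35% (bell-shaped). In the simulation, power for the unadjusted, cut-age and continuous-age models was 90.1%, 90.9% and 91.0% at R² 5%, and 90.3%, 94.4% and 94.9% at R² 20%. Using age in years instead of the cut thus adds about 0.1 to 0.5 points.

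**The case against.** The strongest reply is that nothing the plan promises is missed. Randomisation makes the unadjusted test valid, its interval already allows for chance imbalance, and its power was planned without adjustment. The 53 per group is what remains after the largest planned loss. Nearer 70 the power is already 96.3%, and the gain shrinks to 0.7 to 1.9 points. The adjusted ratio will also be reported and any difference discussed, so the proposal mostly changes which estimate decides. Linear age brings an assumption of its own. All of this stands, and it limits the point to an optional improvement.

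Three stronger readings are tempting and not supported:

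- A reader might infer that the sponsor regards sex and age as affecting TNA. Protocol 10.5.3 speaks only of a possible impact of imbalance, and no section gives an effect size.
- A reader might infer that the exploratory check fails at its own purpose because the cut at 30 ignores age differences within bands. The cut matches the 18-30 and 31-45 bands by which the plan defines balanced recruitment. Imbalance within bands is not what the check is stated to examine.
- A reader might take the 25% as titre variance, or attach it to the deciding test. It is variance of age, in the exploratory model only, under an assumed flat age distribution.

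The reply does not remove the core: the covariates are already collected, the plan already thinks them worth adjusting for, and the deciding model is the place where adjustment would count.

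**Conclusion.** The point holds as a modest gain in precision and robustness. The deciding regression omits two baseline covariates that the plan names and collects, although the allocation does not balance them. At 53 per group the gain is 1.3 to 3.9 power points, with a 2.5% to 8% narrower interval, for R² of 5% to 15%. At 70 per group it is 0.7 to 1.9 points. Every one of these figures rests on an assumed R²; if sex and age explain almost nothing, the gain is almost nothing.

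The documents do not support calling the unadjusted test biased, invalid or underpowered. That judgement rests on randomisation. The Immunogenicity Population is selected after randomisation, and its antibiotic-dose criterion applies only to Groups 1 and 2. Whether this shifts the sex or age mix is unknown, but adjustment would deal with the measured part of any shift. The age cut in the exploratory model is a minor matter with a negligible effect on power.

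**What to change.** In protocol 10.5.2 and SAP 7.2, prespecify sex and age in years as covariates in the formal log10 NF50 regression, and take the adjusted GMT ratio and its 95% CI as the result compared with 0.5. Keep the unadjusted ratio as a named sensitivity analysis. Align SAP 4.6 and the closing sentence of SAP 7.2.1 with this.

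Optionally, use age in years in the exploratory model of protocol 10.5.3 and SAP 7.2.1, and keep the two age bands for the descriptive subgroup tables.

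The cost is a wording change in both documents, one line of code and two degrees of freedom. No new data are needed and the sample size does not change. The change should be made before the SAP is finalised ahead of database lock.

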10.6. Safety Analysis

All safety data will be presented in the form of tabulations and listings, based on the Safety Population. Data summaries will be tabulated by treatment group (Ciprofloxacin only, AV7909 + ciprofloxacin, Doxycycline only, AV7909 + doxycycline, AV7909 only, and Total, ie, all participants receiving any IP) as specified in [Section 10.3](#). Continuous variables will be summarized using number of participants (n), mean, standard deviation (SD), median, minimum, and maximum. Categorical variables will be summarized by the number (frequency) and percentage in each category. No formal hypotheses testing will be conducted for safety data.

10.6.1. Adverse Events

All AEs will be coded to SOC and PT according to MedDRA. Treatment-emergent adverse events (TEAEs) are defined as AEs that present after the initiation of treatment or any AEs already present that worsen in either intensity or frequency following treatment. The incidences of TEAEs will be presented in tabular form by MedDRA coded terms of SOC and PT, and by severity (toxicity grade), seriousness, relationship to IP, and outcome (death, discontinuation of IP, study withdrawal) for each treatment group. A tabulation will be provided of TEAE incidences by MedDRA PT in decreasing frequency of the “AV7909 Total” column. Separate tabulations by MedDRA SOC and PT will be provided for SAEs and AESIs determined to be of autoimmune etiology based on decision of the DSMB. Participants having the same TEAE more than once will be counted in tabulations once for each PT and once within each SOC at the maximum severity and relatedness. The incidences of AEs from the first dose of any IP through the Final Study Visit (Day 51 ± 1d), as well as incidences of AEs from the first dose of any IP up to 12-month follow-up will be tabulated separately as appropriate.

10.6.2. Clinical Laboratory Data

Safety clinical laboratory results will be tabulated by visit and group and listed by individual participant. Observed values and changes from baseline of continuous laboratory variables (hematology, serum chemistry, and selected urinalysis parameters [eg, specific gravity]) will be summarized using descriptive statistics (n, mean, median, SD, minimum, and maximum). Observed values of categorical laboratory variables (eg, urinary protein), incidences of abnormalities by analyte according to laboratory normal ranges and highest toxicity grade (refer to [Table 13 in Appendix A](#)), and shifts from baseline will be summarized descriptively (number and percentage) by visit and treatment group. Shift tables will be produced to reflect shifts from baseline values against the lab normal ranges (low, normal, high) as well as against toxicity grading criteria (Grade 0, Grade 1, Grade 2, Grade 3, Grade 4). Note: Grade 0 = laboratory value within normal range or laboratory value does not meet criteria for toxicity of at least Grade 1

AV7909 Anthrax Vaccine

IND 014451

Protocol EBS.AVA.210, Version 3.0 (28 October 2019)

(refer to [Table 13](#) in [Appendix A](#)). Screening (serology, urine drug screen, FSH) and pregnancy test results will be listed by individual participant.

In tabulations, the last measurement before the first IP administration will be used as the baseline value. In listings, laboratory values outside of the reference range will be flagged: L=low compared to the lower limit of the normal range, H=high compared to the upper limit of the normal range. Additionally, laboratory abnormalities associated with a severity grade based on the toxicity grading criteria (refer to [Table 13](#) in [Appendix A](#)) will be flagged: Grade 1 = Mild, Grade 2 = moderate, Grade 3 = severe, and Grade 4 = potentially life-threatening. Grade 3 or higher laboratory abnormalities will be summarized in a separate listing.

10.6.3. Physical Examination

Complete PE and symptom-directed PE data will be tabulated (number of participants with normal/abnormal findings by body system and group) and listed by individual participant.

10.6.4. Vital Signs

Vital signs data will be tabulated by visit and treatment group and listed by individual participant. Observed values and changes from baseline in vital signs will be summarized descriptively (n, mean, median, standard deviation, minimum, and maximum; incidence of abnormality according to highest toxicity grade). Baseline is defined as the last measurement before the first IP administration. In listings, vital sign abnormalities associated with a severity grade based on the toxicity grading criteria (refer to [Table 12](#) in [Appendix A](#)) will be flagged: Grade 1 = mild, Grade 2 = moderate, Grade 3 = severe, and Grade 4 = potentially life-threatening.

10.6.5. Prior and Concomitant Medications

Medications will be coded according to the World Health Organization's (WHO) WHO Drug Global Dictionary and daily dosages normalized. Data will be tabulated and listed by individual participant according to study period (prior medications taken before the first IP administration, concomitant medications taken after the first IP administration) and treatment group.

10.6.6. Other Safety Variables

10.6.6.1. Reactogenicity

In-clinic and e-diary reactogenicity data will be tabulated using descriptive statistics (number and percentage of participants reporting a reaction) for any symptom and each individual symptom by vaccination, treatment group, and severity grade. During the assessment period post each vaccination, when the severity differs across the daily assessments for a symptom, the maximum severity will be shown in summary tables.

10.6.6.2. Autoantibody Testing and TSH Assessment

Samples taken for TSH assessment and for RF, ANA and anti-ds DNA antibodies will be banked and will only be tested if medically indicated (ie, as per PI's discretion based on a report of

AV7909 Anthrax Vaccine
IND 014451
Protocol EBS.AVA.210, Version 3.0 (28 October 2019)

potential AESI). Results will be tabulated with negative/positive results by study visit and listed by individual participant.

10.7. Interim Analysis

No interim analyses are planned in this study.

10.8. Multiplicity

In this phase 2 study, multiplicity adjustment is not planned. All the PK and immunogenicity endpoints are evaluated in parallel for the two antibiotics, ciprofloxacin and doxycycline.

The primary PK endpoints for each antibiotic will be met when the 90% CIs of the geometric mean of ratios for both AUC_{0-12h} and C_{max} are contained entirely within the equivalence bounds of [0.8, 1.25]. Since both parameters must satisfy the equivalence condition and each equivalence test is conducted at 5% level, the overall type I error rate is controlled at less than 5%.

For immunogenicity, non-inferiority is evaluated as a one-sided test at 2.5% level. As a secondary endpoint, the test will only be formally evaluated when the corresponding primary PK endpoints have been met. Otherwise the results will be provided for information. No adjustment for multiplicity is required based on the closed test procedure.

No other formal hypothesis testing will be carried out. The secondary PK endpoints (single dose) will be evaluated and reported for information only.

10.9. Final Analysis Plan

A Statistical Analysis Plan (SAP) will be finalized prior to clinical database lock [to include data up to and including last subject's last in-clinic visit (Day 51; ie, four weeks after second vaccination)]. Clinical Study Report (CSR) will be generated with data up to and including last subject's last in-clinic visit (Day 51). All data after Day 51 (ie, data up to and including last subject's 12-month safety follow up telephone call) will be included as an addendum to the CSR. Details of the statistical methods and analyses will be provided in the final SAP.

11. DATA HANDLING AND RECORD KEEPING

11.1. Source Documents and Access

Source documents are defined as the records of original observations and activities of a clinical investigation. Source documents will include but are not limited to screening logs, progress notes, clinical and office charts, hospital records, pharmacy dispensing records, laboratory notes, e-diary data, safety laboratory data including both local and central laboratory data, memoranda, and recorded data from automated instruments. All source documents pertaining to this trial will be maintained by the PI(s) and made available for direct inspection and copying by authorized persons. Investigator(s)/institution(s) will permit trial-related monitoring, audits, IRB/IEC review, and regulatory inspection(s) by providing direct access to source data/documents by authorized persons as specified in the ICF.

11.2. Data Management

A validated, electronic data capture (EDC) system will be used during the trial. The data management functions for the study will be outsourced to a CRO. Data management activities to be performed for the study will be described in detail in the Data Management Plan documents. The standard operating procedures (SOPs) governing data management activities will be mutually agreed upon by the CRO and Emergent and documented in these DMP documents. Emergent is responsible for the oversight and management of the CRO.

11.3. Data Collection and Discrepancy Management

Data collected during the study will be recorded in the eCRFs designed for this study. Investigational sites will have the responsibility for capturing and maintaining accurate eCRF data, records, and relevant source documentation, as well as conforming to procedures established by the CRO/Emergent around system access/security and ensuring a data audit/edit trail for data corrections. All source documents will be verified by the CRO study monitor for accuracy. Information from external sources such as laboratory data, images, etc. as defined in this protocol will be collected and maintained outside the EDC and reconciled with the eCRF data periodically. As data are entered into the eCRF, automated edit checks will validate data. Additionally, manual reviews will be performed for data discrepancy by the CRO and queries will be generated into the EDC system. After clinical sites respond to queries and data corrections are made and reviewed by the CRO, the PI will review and electronically sign the eCRF for each participant. The CRO and Emergent will review data for accuracy, completeness, and consistency during the conduct of the study and prior to database lock.

11.4. File Management at the Investigational Site

The PI will ensure that the trial center file is maintained in accordance with the ICH Guideline and as required by applicable local regulations. The PI/institution will take measures to prevent accidental or premature destruction of these documents.

AV7909 Anthrax Vaccine

IND 014451

Protocol EBS.AVA.210, Version 3.0 (28 October 2019)

11.5. Record Retention at the Investigational Site

Per ICH guidelines, study documents will be retained for one of the following periods:

- A period of at least two years after the date of the last approval of a marketing application in an ICH region until there are no pending or contemplated marketing applications;
- A period of at least two years after Emergent has notified the regulatory authority(ies) that clinical investigation with this product is discontinued.

The PI must not dispose of any records relevant to this trial without either (1) written permission from Emergent or (2) provision of an opportunity for Emergent to collect such records. The PI will be responsible for maintaining adequate and accurate electronic or hard copy source documents of all observations and data generated during this trial, including any data queries received from the Sponsor or designee. Such documentation is subject to inspection by Emergent and relevant regulatory agencies. If the PI withdraws from the trial (eg, due to relocation or retirement), all trial-related records will be transferred to a mutually agreed upon designee within an Emergent-specified timeframe. Notice of such transfer will be given to Emergent in writing.

11.6. Protocol Deviations

The PI or site staff may not deviate from the protocol except, in rare circumstances, as necessary to eliminate immediate hazards to the trial participants. In such event, both the Sponsor and IRB/IEC will be immediately notified, no more than 24 hours after the deviation is implemented.

It is the responsibility of the PI to comply with the protocol. A deviation occurs when site personnel or a participant does not adhere to the protocol's stipulated requirements, whether inadvertently or planned. The occurrence of protocol deviations will be routinely monitored by the CRO and Sponsor for evaluation of PI compliance with the protocol, GCP, and regulatory requirements. The PI or designee will inform the IRB/IEC of all protocol deviations according to the requirements of each IRB/IEC. Deviations may be identified during the course of the study by the PI or site staff, study monitor during routine or directed monitoring visits (recorded in monitoring reports), and Sponsor or BARDA personnel. In compliance with GCP, all identified protocol deviations will be documented – entered in the CRO's Clinical Trial Management System or equivalent – and classified according to procedures outlined in the protocol deviation plan. Deviations will be assessed by the CRO and Sponsor to identify appropriate corrective and preventive actions and followed up to ensure renewed understanding and proper execution of the protocol.

In the event of a significant deviation from the protocol due to an emergency, accident, or mistake (eg, violation of informed consent process, participant dosing error, treatment assignment error, participant enrolled in violation of eligibility criteria, violation of concomitant medication use restriction), the PI or designee will contact the MM at the earliest possible time by telephone, or the reverse as applicable. The PI and MM will come as quickly as possible to a joint decision regarding the participant's continuation in the trial. This decision will be documented by the PI and MM and reviewed by the site monitor.

AV7909 Anthrax Vaccine

IND 014451

Protocol EBS.AVA.210, Version 3.0 (28 October 2019)

Continued protocol deviations despite re-education of investigational site personnel, or persistent protocol deviations that are reportable to regulatory agencies may result in discontinued shipment of IP and termination of further enrollment at the investigational site, or termination of the investigational site from the study.

